#### Study aim:

The purpose of this study is to investigate the effects of substituting sitting under free-living conditions in South Asian adults with overweight and obesity on continuous glucose profiles.

#### Methods

##### Study overview

This was a randomised crossover design study with two activity regimens (SIT and SITless) undertaken in free-living conditions. The study was conducted according to the Declaration of Helsinki principles and approved by the University of Bedfordshire Institute for Sport and Physical Activity Research Ethics Committee (2020ISPAR006). Participants provided written informed consent to take part. The study was conducted and reported in line with the Consolidated Standards of Reporting Trials guidance. The trial was registered with [clinicaltrials.gov/\(NCT04645875\)](https://clinicaltrials.gov/ct2/show/study/NCT04645875). Experimental regimen order was randomised using an online computer-generated randomisation method (<https://www.randomizer.org/>). Following a preliminary testing visit and successful try-out-day, participants completed two experimental regimens, each lasting 4 days, with a 3 day washout period between to minimise potential carryover effects.

##### Participants

South Asian adults living in the UK aged 18 to 75 years living with overweight or obesity ( $\text{BMI} > 23 \text{ kg m}^{-2}$ ) were eligible to take part. The BMI thresholds were aligned with overweight/obesity-related comorbidities among South Asian populations and calculated as  $\text{body mass (kg)}/\text{height (m)}^2$ . 'South Asian' was defined as anyone identifying themselves as South Asian or British South Asian. Exclusion criteria were self-reported CVD, current diagnosis of COVID-19, diabetes, a known blood-borne disease, pregnancy, recent or current smoker and other health issues (e.g., neurological disorders) or physical limitations that might limit the ability to perform the required volume of LPA. Participants were recruited from the local community (Luton and Bedford, UK) using adverts through social media posts (e.g., Facebook and Twitter) and distribution of flyers.

##### Sample size calculations

A-priori sample size was calculated using G\*Power version 3.0.10. The primary outcome was postprandial glucose ( $\text{mmol L}^{-1}$ ) with the mean effect size taken from previous lab-based studies in participants with overweight and obesity ( $d = 0.9$ ; Dey et al. 2024; Dunstan et al. 2012; Henson et al. 2016). A total of 11 South Asian individuals living with overweight/obesity were required to achieve 80% power with an alpha value of 5%. Recruitment targeted 14 participants to allow for 20% dropout.

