**Please make sure you continue your normal daily life during the 3 days between your “Sit Less” and “Sit” regimens.**

## Statistical analysis plan

Statistical analyses were performed using SPSS version 26.0 (SPSS Inc., Armonk, N.Y., USA). Data were tested for normality using Q-Q plots. Linear mixed models with a compound symmetry correlation structure were used to determine the main effect of experimental regimen (SIT vs. SITless) for the outcome variables, with experimental regimen included as a fixed factor and participants included as a random factor. The models analysing activPAL outcomes were adjusted for activPAL wear time. The models analysing FGM outcomes adjusted for BMI. Two-tailed statistical significance was set at  $p \leq 0.05$ . Cohen's d effect sizes were calculated, with 0.2, 0.5, and 0.8 indicating a small, medium or large effect, respectively (Cohen 1988). All data are presented as mean (95% confidence interval [CI]) unless stated otherwise.

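### On the printed inputs (d = 0.9 read as the paired effect size, two-tailed 5%), 11 completers give about 77% power rather than 80%, and 12 are needed; the paragraph does not print what would reproduce 11

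*Combined protocol and SAP*

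**What the plan says.** The section on sample size calculations says that G\*Power 3.0.10 was used, with d = 0.9 for postprandial glucose. That value is described as the "mean effect size taken from previous lab-based studies in participants with overweight and obesity", averaged over three cited studies. It then states: "A total of 11 South Asian individuals living with overweight/obesity were required to achieve 80% power with an alpha value of 5"%. The recruitment figure follows: "Recruitment targeted 14 participants to allow for 20% dropout".

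Two other places fix the type of comparison. The study overview says "This was a randomised crossover design study with two activity regimens (SIT and SITless) undertaken in free-living conditions", so each participant supplies both conditions and the comparison is paired. The statistical analysis plan says "Two-tailed statistical significance was set at" p ≤ 0.05.

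The sample size section does not give the test family chosen in the software, the number of tails used in the calculation, the unrounded effect size, or a within-person correlation. It does not say whether d was standardised by the SD of the paired differences or by the SD within a condition.

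**The concern.** A power statement should be reproducible from the inputs printed beside it. Here the natural reading is a paired, two-tailed test at 5% with d = 0.9, and on that reading 80% power needs 12 completers. The figure of 11 falls one short.

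What is at stake is the accuracy of a stated design property. At 11 completers the chance of missing an effect of the assumed size would be about 23% rather than 20%. With so few participants, one person more or less moves power by about four points, so the inputs need to be stated precisely enough for the number to be checked.

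**Working it through.** **Inputs.** d = 0.9, N = 11, power 80%, alpha 5%, 20% dropout and 14 recruited come from the sample size section. The paired comparison comes from the study overview. Two tails come from the statistical analysis plan. One assumption is added: 0.9 is the paired effect size d_z (mean difference divided by SD of differences) and is exactly 0.90.

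**Formula.** For a paired t-test with n completers, the test statistic is noncentral t with df = n − 1 and noncentrality d_z × √n. Power is the probability that it falls outside ± t(0.975, n − 1).

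**Attempt to reproduce 11.** At n = 11, the noncentrality is 0.9 × √11 = 2.985 and the critical value on 10 df is 2.228. Power is 76.7%. At n = 12, the noncentrality is 0.9 × √12 = 3.118, the critical value on 11 df is 2.201, and power is 81.0%.

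| Completers | Power at d_z = 0.90, two-tailed | Smallest d_z with 80% power |
|---|---|---|
| 10 | 71.7% | 1.00 |
| 11 | 76.7% | 0.94 |
| 12 | 81.0% | 0.89 |
| 14 | 87.5% | 0.81 |

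**Other routes at d_z = 0.90.** None of these gives 11.
- One-tailed 5%, exact t: 79.3% at 9 and 83.6% at 10, so 10.
- Two-tailed normal approximation: ((1.960 + 0.842)/0.9)² = 9.69, so 10.
- Residual df of n − 2, as with a period term: 75.7% at 11 and 80.2% at 12, so 12.

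**Routes that do give 11.**
- *Rounding.* 80% power at n = 11 needs d_z of at least 0.938. Values from 0.938 to 0.949 print as 0.9 and give 80.0% to 80.9%. Rounding can also work the other way: at d_z = 0.85, 13 are needed (80.3%).
- *Type of d.* If 0.9 is a between-condition d and the within-person correlation is r, then d_z = 0.9/√(2(1 − r)).

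| r | d_z | Power at 10 | Power at 11 |
|---|---|---|---|
| 0.40 | 0.822 | 63.9% | 69.1% |
| 0.50 | 0.900 | 71.7% | 76.7% |
| 0.54 | 0.938 | 75.2% | 80.1% |
| 0.59 | 0.994 | 79.8% | 84.3% |
| 0.60 | 1.006 | 80.8% | 85.2% |

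So 11 is the smallest sufficient number for r of about 0.54 to 0.59. At r = 0.50, d_z equals d by construction, so a repeated-measures calculation with that correlation repeats the 76.7% and is not separate confirmation of it.

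**Dropout.** 11/0.8 = 13.75, which rounds up to 14, as stated. If 12 replaced 11, 12/0.8 = 15. With 14 recruited, two dropouts leave 12 (81.0%) and three leave 11 (76.7%).

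**The case against.** The strongest reply is that the calculation may have been right. The effect size is an average printed to one decimal, and its type is not stated. An average of 0.94, or a between-condition 0.9 with a correlation near 0.55, gives exactly 11 in a two-tailed test. The documents exclude neither. This stands, and it limits the point: one can say that 11 does not follow from what is printed, but not that the sponsor miscalculated. The reply does not restore reproducibility, because neither value appears in the plan.

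A second reply is that the gap is small: one participant, 3.3 points of power, and a recruitment target that gives 87.5% if all 14 complete. This also stands, and it is why the point is minor.

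Three stronger readings are tempting and are not supported.
- A reader might infer a second error in the recruitment target. There is none: 14 is the correct inflation of 11, and 15 arises only after 11 has been replaced by 12.
- A reader might infer that power is lower still because d comes from laboratory studies and this trial is free-living. The section discloses that origin openly. Whether the effect carries over is a judgement about the assumption, and the documents give no free-living effect size to test it. It has no bearing on whether 11 matches d = 0.9.
- A reader might infer that a null result would be over-read. A difference between 77% and 80% is too small to carry that, and nothing in the plan describes such an interpretation.

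**Conclusion.** The point holds as a conditional one. With d_z = 0.90 and a two-tailed 5% paired test, 11 completers give 76.7% power, and the stated 80% is first reached at 12 (81.0%). The type II error at 11 is 23.3% rather than 20%.

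The arithmetic is certain given those inputs. What is uncertain is whether 0.9 is the exact paired value, and confidence in the point depends on that. If the sponsor holds an unrounded d of about 0.94, or used a correlation of about 0.54 to 0.59, then 11 is right and what remains is missing detail in the text. Severity is minor under either explanation.

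**What to change.** If 0.90 is the paired effect size that was used, restate the section along these lines:

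> Eleven completers give 77% power and 12 give 81% for a paired d of 0.9 (two-tailed 5%); 14 recruited keep at least 80% power if no more than two drop out. The smallest paired d detectable with 80% power is 0.94 with 11 completers, 0.89 with 12 and 0.81 with 14.

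If the calculation used an unrounded d or a correlation that yields 11, keep 11 and print that value and the type of d instead. The text should not describe 0.9 as the paired d unless it was. In either case, add the test family and the number of tails. The detectable effects at 11, 12 and 14 hold however the 0.9 arose and can be added regardless.

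The cost is a few sentences. No extra participants and no change to the analysis are needed. If 0.90 is the paired value, the headline figure becomes slightly less favourable.

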##### Detailed Description:

Anthropometric measurement tools, including a stadiometer, a measurement tape and a digital weighing scale, an activity monitor and a Flash Glucose Monitor and sensor, were posted to the participants' home or workplace or the research team dropped all these items at participants' doorstep to allow participants to

take their measures including height, weight, and waist circumference.

Participants performed a try-out day of the SITless regimen after preliminary testing and before the first experimental regimen. Participants were only eligible for inclusion if they were able to adhere to the experimental protocol (i.e., substitute a minimum of 5-h/day sitting with  $\geq 2$ -h of self-perceived light walking and  $\geq 3$ -h of standing), assessed via monitoring with an activPAL. Participants were provided with a second attempt if required.

After the try-out day, participants were set up with the FGM and activPAL, which were both worn throughout the experimental period. Setup was completed 24-h before the commencement of the first experimental regimen and subsequently worn for 11 days (i.e., 2\* 4-day regimens and 3 days washout). Regimen 1 (SIT or SITless) took place over 4 days (day 1-4: Monday to Thursday), followed by a 3-day washout period (day 5-7: Friday to Sunday), followed by regimen 2 (SIT or SITless) for 4 days (day 8-11: Monday to Thursday). Participants were informed of the order of their experimental regimens and provided verbal and written guidance on how to complete the protocols. The experimental regimens were as follows:

**SIT regimen:** Participants were instructed to restrict walking to  $\leq 1$  h/day and standing to  $\leq 1$  h/day during their waking day. Participants were allowed to perform their daily activities, including cooking and other household activities, within the 2-h of permitted walking and standing (instruction is attached below).

**SITless regimen:** Participants were instructed to substitute a minimum of 5-h/day sitting with  $\geq 3$ -h of standing and  $\geq 2$ -h of self-perceived LPA in addition to interrupting their sitting for 2-5-min every 30-min. A list of activities (including walking at a slow pace, walking on the spot, jumping up and down, and standing) was provided as examples of activities that participants could perform during this regimen. Participants received feedback on their non-sitting time and the number of light and moderate-intensity steps from the try-out day. They were guided towards achieving compliance in this regimen by identifying potential activities they could engage in to interrupt sitting, reviewing their number of sitting interruptions and aiming to accumulate approximately 12,000 steps per day (6,000 steps being equivalent to 1-h of moderate-intensity walking) (instruction is attached below).

Participants were asked to refrain from food and drink containing alcohol for 24-h before and to avoid performing structured exercise for 48-h before the experimental protocol commenced and throughout the entire experimental period (a total of 11-days). A kitchen scale was provided so participants could weigh and record all food and beverage consumption in a diary during the first 4-day regimen and replicate this dietary intake exactly during the second 4-day regimen. Participants were instructed to consume a standardised diet (at least 50% carbohydrate) in order to reduce dietary heterogeneity within the study population. Participants were advised that the meals were spaced evenly throughout the day with 3 to 4-h intervals, with snacks consumed between meals to ensure three distinct and consistent glucose responses across each day.

### SIT Regimen Instructions

Dear Participant,

During the Sit regimen, we want you to sit as much as possible. Please follow these instructions from dates [..... ] to [..... ]

1. Please limit standing to a maximum of **1 hour per day** and walking to a maximum of **1 hour per day** for each of the 4 days. Spend the rest of the day sitting down. **This is really important as we can then see how the Sitless regimen affects your health compared to days when you sit down a lot.** Where possible please use public transport or a car to travel to and from places to limit your activity levels.

**Please do not engage in any structured exercise (e.g., cycling, sports, gym workout, running session etc.) or consume any alcohol during the whole study.**

**Please make sure you continue your normal daily life during the 3 days between your “Sit Less” and “Sit” regimens.**

## **SITless Regimen Instructions**

Dear Participant,

During the Interrupting Sitting condition, you will be asked to follow the below instructions for each of the 4 days. This will take place on dates [...] to [...]

Each day please substitute a minimum of 5 hours per day of sitting with  $\geq 2$  hours of light-intensity physical activity and  $\geq 3$  hours of standing breaks. Try to spread this out over the whole day. In addition, you should try to rise from the seated position for 2-5 minutes every 30 minutes to engage in standing/light-intensity physical activities to interrupt your sitting.

If you have a long commute to work, need to sit through a long meeting, or cannot stand within a particular hour for a different reason, that is ok as long as you replace your sitting time with at least **5** hours of standing and light activity over the day.

**Please ensure you engage in a minimum of 3 hours of standing and 2 hours of light-intensity physical activity (e.g. from the activities below) on each of the 4 days.**

Here are some suggestions for activities you can do during your breaks:

- Walking at a slow pace
- Walking on the spot
- Jumping up and down
- Taking the stairs
- Standing (you could stand when you are unable to engage in the other activities e.g. during meetings)

**You will have been given a demonstration by the research team virtually. Tips to**

**remember to take your breaks**

1. Download a phone app to remind you e.g.
  - a. Stand Up! The Work Break Timer (Apple - recommended)
  - b. Break Reminder (Android)
  - c. Goodtime Productivity timer (Android - recommended)
2. Download a computer app that sends reminders to your screen e.g.
  - a. WorkRave (Windows – recommended)
  - b. PC Workbreak (Windows)
  - c. Time Out (Mac – recommended)
  - d. Awareness (Windows or Mac)
  - e. Break Timer (available on Chrome browser)
3. Set reminders on your phone, computer or outlook calendar
4. **You may want to tally up how many breaks you have taken each day too!**

5. Download a phone app to remind you e.g.
  - a. Stand Up! The Work Break Timer (Apple - recommended)
  - b. Break Reminder (Android)
  - c. Goodtime Productivity timer (Android - recommended)
6. Download a computer app that sends reminders to your screen e.g.
  - a. WorkRave (Windows – recommended)
  - b. PC Workbreak (Windows)
  - c. Time Out (Mac – recommended)
  - d. Awareness (Windows or Mac)
  - e. Break Timer (available on Chrome browser)
7. Set reminders on your phone, computer or outlook calendar
8. **You may want to tally up how many breaks you have taken each day too!**

**Please do not engage in any structured exercise (e.g., cycling, sports, gym workout, running session etc.) or consume any alcohol during the whole study.**

**Please make sure you continue your normal daily life during the 3 days between your “Sit Less” and “Sit” regimens.**

## Statistical analysis plan

Statistical analyses were performed using SPSS version 26.0 (SPSS Inc., Armonk, N.Y., USA). Data were tested for normality using Q-Q plots. Linear mixed models with a compound symmetry correlation structure were used to determine the main effect of experimental regimen (SIT vs. SITless) for the outcome variables, with experimental regimen included as a fixed factor and participants included as a random factor. The models analysing activPAL outcomes were adjusted for activPAL wear time. The models analysing FGM outcomes adjusted for BMI. Two-tailed statistical significance was set at  $p \leq 0.05$ . Cohen's d effect sizes were calculated, with 0.2, 0.5, and 0.8 indicating a small, medium or large effect, respectively (Cohen 1988). All data are presented as mean (95% confidence interval [CI]) unless stated otherwise.

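### The two-period crossover model has no period term, so a week-1 to week-2 shift would cost power or, if the realised orders are unequal, bias the regimen estimate

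*Combined protocol and SAP*

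**What the plan says.** The Study overview sets the design: "This was a randomised crossover design study with two activity regimens (SIT and SITless) undertaken in free-living conditions". On allocation it says "Experimental regimen order was randomised using an online computer-generated randomisation method". It states no blocking, ratio or other device to equalise the two orders, and no number per order. A 3-day washout is included, aimed at carryover.

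The Statistical analysis plan gives the model: compound symmetry, "with experimental regimen included as a fixed factor and participants included as a random factor". Two covariates are added: "The models analysing FGM outcomes adjusted for BMI", and "The models analysing activPAL outcomes were adjusted for activPAL wear time". Tests are two-tailed at 5%. No term for period, order or sequence appears in the documents.

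Two design features in the Detailed Description follow calendar order and not regimen. Participants record intake in a "diary during the first 4-day regimen and replicate this dietary intake exactly during the second 4-day regimen". The glucose sensor and activPAL are fitted once, 24 hours before the first regimen, and worn for 11 days, so first-period data come from days 1-4 and second-period data from days 8-11.

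**The concern.** In a two-period crossover each within-person difference carries the regimen effect plus or minus any shift between the weeks, the sign depending on order. A period term removes that shift. Without one, the shift goes to one or both of two places. With equal orders it cancels from the estimate but stays in the residual, so the standard error is too large and the test conservative. With unequal orders part of it also enters the regimen estimate.

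The covariates do not do this job. BMI takes one value per person, so with complete data it cannot change the within-person contrast. Wear time may differ between weeks, but it is not an indicator of period.

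At stake is the precision of every regimen contrast in a trial of 11 to 14 people and, for a lopsided split, the accuracy of the one estimate that readers will see.

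**Working it through.** **Inputs from the documents.** Effect size d = 0.9, 80% power, 5% alpha, 11 required, 14 recruited to allow for 20% dropout (Sample size calculations); two-tailed 5% test and model terms (Statistical analysis plan).

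**Assumptions.** d is the standardised paired difference (the plan does not say which d it is). Each person contributes one value per regimen. The shift is 0.5 SD of the paired difference, with 0 and 0.3 SD for range. Randomisation is simple wherever a split probability is given.

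**The plan's own figure.** A paired t-test with d = 0.9, two-sided 5%, has power 76.7% at 11 and 81.0% at 12. One-sided, 10 gives 83.6%. The stated 11 lies within one participant of the two-sided answer and of the one-sided answer, which is close enough to use. Dropout: 11/0.80 = 13.75, so 14, as stated.

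**Model.** Let D = SITless minus SIT for one person, with SD 1 apart from the shift. Then D = tau + pi × s + e, where tau is the regimen effect, pi is the second-week minus first-week shift, and s = +1 if SITless came second and -1 if it came first. Let n1 people have s = +1 and n2 have s = -1, with n = n1 + n2.

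- Without period, the estimate is the mean of D: bias = pi × (n1 - n2)/n, and the variance of D gains pi² × [1 - ((n1 - n2)/n)²].
- With period, the estimate is the average of the two order-specific means: no bias, SE = ½ × √(1/n1 + 1/n2), on n - 2 degrees of freedom.

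**Bias as a share of the shift.** 7:7, 0; 6:5, 1/11 = 9%; 9:5, 4/14 = 29%; 10:4, 6/14 = 43%; 8:3, 5/11 = 45%.

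**Effect of a 0.5 SD shift, by simulation (true effect 0.9 for estimates and power, 0 for alpha).**

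| Split | Estimate, no period term | Alpha, no period term | Power, no period term | Power, with period term |
|---|---|---|---|---|
| 7:7 | 0.90 | 3.0% | 81% | 87% |
| 10:4 | 1.11 or 0.69 | 8.3% | 95% or 58% | 80% |
| 6:5 (shift and effect in the same direction) | 0.95 | 3.0% | 73% | 75-76% |
| 8:3 | 1.13 or 0.67 | 7.4% | 88% or 44% | 66% |

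Paired entries depend on the direction of the shift. The higher unadjusted power at 10:4 or 8:3 reflects an inflated estimate and is not a gain. With the period term the estimate is 0.90 and alpha 5% throughout.

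At the same shift, alpha without a period term is 3.5% at 8:6 and about 5% at 9:5. At 0.3 SD, 10:4 gives about 6.4%.

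**Chance of each kind of split of 14 under simple randomisation.** 7:7: 3432/16384 = 21%. 9:5 or worse: 6946/16384 = 42%. 10:4 or worse: 2942/16384 = 18%. With 11 completers an equal split is impossible, and 8:3 or worse has probability 23%.

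**Averaged over simple randomisation, no period term, 0.5 SD shift.** Mean estimate 0.90, alpha about 5%. Power falls from 87.6% to 79.5% at 14 and from 76.8% to 67.2% at 11.

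**Cost of the term when there is no shift.** At 7:7 the SE is unchanged (0.267) and one degree of freedom goes: 87.5% to 87.0%. At 6:5: 76.7% to 75.4%. At 10:4 the SE rises from 1/√14 = 0.267 to ½ × √(1/10 + 1/4) = 0.296: 87.5% to about 80%. At 8:3: 76.7% to 66%.

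**The case against.** Four objections have force.

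First, order was randomised. A reader might infer that the regimen effect is biased or its false-positive rate inflated. The documents do not support that. Averaged over simple randomisation the estimator is unbiased with alpha about 5%; bias arises only given an unequal realised split, and the split is not reported.

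Second, a reader might take 42%, the chance of 9:5 or worse, as the chance of an inflated test. At a 0.5 SD shift, alpha at 9:5 is still about 5%. Among splits of 14 it is clearly above 5% only at 10:4 or worse, an 18% chance, and that figure assumes simple randomisation. Balance is unstated, not shown to be absent. The impossibility of equal orders at 11 matters little in itself: at 6:5 and 0.5 SD the bias is 0.5/11 = 0.045 SD, or 5% of 0.9.

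Third, no shift is reported or quantified. Both periods run Monday to Thursday, a SITless try-out day precedes the first, and copying the diet is meant to equalise intake. The documents say nothing of sensor readings changing with wear. The design leaves room for a shift but does not show one, and a shift near zero does little harm.

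Fourth, the calculation uses one value per regimen, while each regimen lasts 4 days and the plan does not say whether daily or averaged values are analysed. Nor does it model the activPAL outcomes with their wear-time covariate. The error rates and power are therefore illustrations for the simplest case. If daily values are used and all days are complete, the bias formula still applies.

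What remains is that the model leaves out a design factor, nothing else in it does that factor's work, and the term costs little when the orders are near equal.

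**Conclusion.** The point holds as a conditional one. The model omits period, and BMI cannot stand in for it. If a shift exists, equal orders leave it in the residual (at 0.5 SD and 7:7: power 81% instead of 87%, alpha about 3%). Unequal orders bias the estimate by 9% of the shift at 6:5 and up to 43% at 10:4, where alpha is 8.3% at a 0.5 SD shift. Over repeated randomisation the loss is in precision only, about 88% to 80% power at 14.

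The sizes rest on an assumed shift, one value per person per regimen, d read as a paired effect and, for the split probabilities, simple randomisation. The documents do not show that a shift occurred, that the orders were unequal, or that the reported effect is wrong. The change should be made as a cheap improvement. The omission does not by itself invalidate the analysis.

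**What to change.** Add period (first or second) as a fixed factor in the glucose and activPAL models, and report the number randomised to each order, with the number analysed if it differs. State how order was balanced, if it was. The trial's records of each person's order supply all that is needed, so the models can be refitted without new data. The text describes randomisation as already done, so advice on blocking the allocation would come too late.

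The cost is one line of the plan and its syntax, and one error degree of freedom. With no shift, the loss of power is about 0.5 points at 7:7, 1.3 at 6:5, 8 at 10:4 and 11 at 8:3. The cost is largest where the unadjusted estimate is most exposed to bias. BMI may be kept or dropped: with complete data it does not change the regimen contrast.
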